# 5.4.8 Hypertension (Dose delays for Ramucirumab only)

Treat with anti-hypertensive medication as needed. The goal of BP control should be consistent with general medical practice Consider increased BP monitoring; Grade 1 start anti-hypertensive medication if (SBP 120-139 mmHg or DBP 80-89 mm Hg) appropriate Grade 2 asymptomatic Begin anti-hypertensive therapy and continue agent (SBP 140-159 mmHg or DBP 90-99 mm Hg) Grade 2 symptomatic Start or adjust anti-hypertensive (SBP 140-160 mmHg or DBP 90-100 mm Hg) medication • Grade 3 Hold agent until symptoms resolve AND BP < 160/90mmHg  $(\geq$  SBP 160 mmHg or  $\geq$  DBP 100 mmHg • Grade 4 Discontinue agent (Hypertensive crisis or malignant hypertension)

Patients who hold or discontinue Ramucirumab due to hypertension may continue other protocol treatment.

5.4.9 Venous Thrombotic Events

Patients should be carefully monitored for evidence of thromboembolic disease during treatment.

- 5.4.9.1 Grade 3 venous thrombosis or asymptomatic pulmonary embolism: Hold Ramucirumab. Ramucirumab may be resumed during the period of full-dose anticoagulation if all of the following criteria are met:
  - The patient must have an in-range INR (usually between 2 and 3) on a stable dose of warfarin or be on stable dose of low molecular weight heparin prior to restarting Ramucirumab treatment;
  - The patient must not have pathological conditions that carry high risk of bleeding (e.g. tumor involving major vessels);
  - The patient must not have had hemorrhagic events while on study.
- 5.4.9.2 Grade 4 or for recurrent/worsening venous thromboembolic events after resumption of Ramucirumab: Discontinue Ramucirumab.
- 5.4.9.3 For symptomatic pulmonary embolism, patients will discontinue all protocol treatment.
- 5.4.10 Arterial Thrombotic Events
  - 5.4.10.1 For Grade 2 arterial thrombotic events not present at baseline or worsened since the initiation of protocol therapy, discontinue Ramucirumab. Patients may continue other protocol treatment.
  - 5.4.10.2 For Grade 3 cerebrovascular ischemia, and/or peripheral or visceral arterial ischemia, discontinue Ramucirumab. Patients may continue other protocol treatment.
  - 5.4.10.3 For Grade 3 cardiac ischemia/infarction, discontinue Ramucirumab. Patients may continue other protocol treatment.
  - 5.4.10.4 For any Grade 4 arterial thrombotic event, including cerebrovascular ischemia, cardiac ischemia/infarction, peripheral or visceral arterial ischemia, discontinue all protocol treatment.
- 5.4.11 Left Ventricular Dysfunction
  - 5.4.11.1 Grade 3 LV dysfunction: Symptomatic CHF responsive to intervention.
    - Discontinue cetuximab (for patients on the control arm) or cetuximab and ramucirumab (for patients on the experimental arm). Patients may continue other protocol treatment.
  - 5.4.11.2 Grade 4 LV dysfunction: Poorly controlled refractory CHF; intervention such as ventricular assist device or heart transplant is indicated.
    - Discontinue all protocol treatment.

- 5.4.12 Hemorrhage/bleeding
  - 5.4.12.1 For Grade 3 hemorrhage/bleeding, permanently discontinue Ramucirumab and hold other protocol treatment; once hemorrhage or bleeding resolves, other protocol treatment may be continued at the treating physician's discretion.
  - 5.4.12.2 For Grade 4 hemorrhage/bleeding, discontinue all protocol treatment.
- 5.4.13 Proteinuria (Dose delays for Ramucirumab only)
  - 5.4.13.1 For proteinuria  $\geq$  2+ or UPC (urinary protein: creatinine ratio) > 1.0: Confirm total urine protein with a 24-hour urine collection. For 2+ proteinuria, the scheduled dose of Ramucirumab may be given while awaiting the results of the 24-hour collection. For > 2+ proteinuria, hold Ramucirumab while awaiting results of the 24-hour urine collection. Other protocol treatment may be continued. If proteinuria is 2-3 g/24 hours, hold Ramucirumab until urine protein recovers to < 2 g/24 hours, then resume at the -1 dose level. Continue other protocol treatment. A second dose reduction (to 5 mg/kg every other week) is permitted if the protein level > 2g/24 hours recurs. Ramucirumab will be discontinued permanently if the protein level is > 3g/24hours, if there is a third occurrence of proteinuria > 2 g/24hours, or if the protein level does not return to < 2g/24hours within 2 weeks.
  - 5.4.13.2 If nephrotic syndrome (Grade 4 proteinuria) occurs, discontinue Ramucirumab.

Grade 3 Rash	Cetuximab	Outcome	Cetuximab Dose Modification
1st	Hold infusion	If improvement:	Continue at current dose
occurrence	1 to 2 wks	If no improvement:	Discontinue cetuximab
2nd	Hold infusion	If improvement:	Reduce one dose level
occurrence	1 to 2 wks	If no improvement:	Discontinue cetuximab
3rd	Hold infusion	If improvement:	Reduce two dose levels
occurrence 1 to 2 wks	If no improvement:	Discontinue cetuximab	
4th occurrence	Discontinue cetuximab		
Grade 4 Rash	Discontinue cetuximab		

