#### Schema

Primary endpoint: PFS; 90% power to detect difference between 4.5 months for control vs. 7.65 months for experimental arm ( $\alpha$  = 0.10,  $\beta$  = 0.10)

\* Treatment should not be started until at least 28 days after last bevacizumab dose.

Rev. 6/14 \*\* Arm B closed to accrual in Addendum #5. New patients are randomized to Arm A or Arm C.

Rev. 6/14 Accrual Goal = 135

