A total of 13 of 24 (54.2%) patients to date have experienced events that were considered possibly, probably, or definitely related (related) to treatment with Ramucirumab. The most common (> 10%) treatment-related events were proteinuria (16.7%), diarrhea (12.5%), and hypertension (12.5%). Adverse events  $\geq$  Grade 3 considered to be at least possibly related to Ramucirumab were reported in three patients and include duodenal ulcer hemorrhage (Grade 4), hypertension, and fatigue.

As of 1 September 2008, 19 patients were evaluable for response; of these patients, 12 have experienced a best overall response of stable disease, including five with  $SD \ge 6$  months. These five patients had cancers of the colon (2 patients), liver (2 patients), and kidney (1 patient). Three of these patients have had ongoing SD for > 10 months duration. Six patients remain on study (two patients in the 10-mg/kg every other week cohort, two patients in the 15-mg/kg every three week cohort, and two patients in the 20-mg/kg every three week cohort).

As of January 18, 2010, at least 454 patients had received at least one dose of IMC-1121B on ImClone sponsored phase 1-2 studies and at least 83 patients had received at least one dose of blinded IMC-1121B/placebo on ImClone sponsored randomized phase III studies. Data safety monitoring committee reviews have been performed regularly on phase 2 studies in melanoma (involving combination with dacarbazine), prostate cancer (involving combination with mitoxantrone/prednisone), ovarian cancer (monotherapy), colorectal cancer (involving combination with mFOLFOX-6) and breast cancer (involving combination with docetaxel).

Some of the published data include:

- a) The Phase 1 Monotherapy Study (Spratlin et al. J Clin Oncol 2010; 28: e-published 4 Jan 2010). 37 patients treated with advanced, refractory solid tumors. Ramucirumab was given weekly as monotherapy. Reported results included PR in 4/27 (15%) patients with measurable disease and PR or SD ≥ 6 months in 11/37 (30%) of patients.
- b) Initial Phase 2 Presentation for metastatic, TKI-refractory Renal Cancer (Garcia et al. ESMO/ECCO Berlin 2009. 40 patients were given ramucirumab 8mg/kg q 2 wk. Of these, 50% had prior sunitinib, 35% prior sunitinib and sorafenib and15% prior sorafenib. The preliminary median PFS is 6 months and 3/40 (7%) had confirmed PR. The drug was well-tolerated.

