# 5.4.1 General Considerations

- a. A new cycle of treatment may begin when the ANC is ≥ 1,500/mcl, the platelet count is ≥ 75,000/mcl, and any treatment-related GI toxicity is resolved to ≤ Grade 1.
- b. If the initiation of a new cycle, or treatment during a cycle is delayed for ≥ 4 weeks, the patient should be removed from protocol treatment.
- c. Held doses are not to be made up.
- d. If one therapeutic agent is permanently discontinued secondary to toxicity, then therapy with the other study agents should continue and the patient should remain on-study with full adherence to all protocol-related requirements
- e. In the event of serious or life-threatening conditions, hold the offending agent. If the patient is to continue on therapy, all agents should be held until the toxicity resolves to grade < 2.

ARM	AGENT	INITIAL DOSE	LEVEL -1	LEVEL -2	
	Cetuximab	500 mg/m 	400 mg/m 	250 mg/m 	
A (IC)	Irinotecan	180 mg/m 	150 mg/m 	120 mg/m 	
B (ICR) Closed to accrual	Ramucirumab	8 mg/kg	6 mg/kg	5 mg/kg	
	Cetuximab	500 mg/m 	400 mg/m 	250 mg/m 	
	Irinotecan	180 mg/m 	150 mg/m 	120 mg/m 	
	Ramucirumab	6 mg/kg	5 mg/kg	4 mg/kg	
C (mICR)	Cetuximab	400 mg/m 	250 mg/m 	200 mg/m 	
	Irinotecan	150 mg/m 	120 mg/m 	90 mg/m 	

f. Dose reductions for all agents are as follows:

**NOTE:** In the event that an agent is given at dose level (-2) and dose modification rules call for further reduction, the agent should be discontinued.

Rev. 12/11, 6/14

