8.3.4 Storage and Stability

> Chemical and physical in-use stability has been demonstrated for up to 24 hours below 25°C (77°F). DO NOT FREEZE OR SHAKE IMC-**1121B.** From a microbiological point of view, the prepared product should be used immediately. If not used immediately, in-use storage time and conditions are the responsibility of the user and would normally not be longer than 24 hours at 2°C - 8°C (36F° - 46°F). IMC-1121B should be protected from light when being stored. In the event

	ECOG-ACRIN Cancer Research Group		E7208 Version Date: March 22, 2016	
Rev. 12/11, 5/16		of a temperature excursion, please contact [name] [contact].		
		Dose Specifics		
Rev. 6/14		8.3.5.1	Arm B (ICR):	
			Patients will receive 8 mg/kg of IMC-1121B every 2 weeks, administered as an I.V. infusion over 1 hour. The dose of IMC-1121B will be dependent upon the patient's baseline body weight in kilograms. This dose will be recalculated if there is a 10% change in body weight from baseline. IMC 1121B is formulated at 10 mg/mL (with a dose of 8 mg/kg).	
			Premedication	
			Premedication is recommended but not required prior to infusion of ramucirumab. Recommended premedication agents include histamine H1 antagonists such as diphenhydramine hydrochloride 50 mg I.V. (or equivalent). Additional premedication may be provided at investigator discretion.	
Rev. 6/14		8.3.5.2	Arm C (mICR):	
			Patients will receive 6 mg/kg of IMC-1121B every 2 weeks, administered as an I.V. infusion over 1 hour. The dose of IMC-1121B will be dependent upon the patient's baseline body weight in kilograms. This dose will be recalculated if there is a 10% change in body weight from baseline. IMC 1121B is formulated at 10 mg/mL (with a dose of 8 mg/kg).	
			Premedication	
			Premedication is recommended but not required prior to infusion of ramucirumab. Recommended premedication agents include histamine H1 antagonists such as diphenhydramine hydrochloride 50 mg I.V. (or equivalent). Additional premedication may be provided at investigator discretion.	
	8.3.6	Preparati	on	
		IMC-1121B drug product are sterile, preservative-free, injectable liquids in single-use 50-mL vials containing 500 mg/50 mL IMC-1121B in a histidine-buffered formulation at a final concentration of 10 mg/mL. Each vial is packaged and labeled in accordance with local regulations.		

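### On Arm C the second ramucirumab reduction for proteinuria reduces nothing: section 5.4.13.1 names 5 mg/kg, which is already that arm's level -1

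*Combined protocol and SAP*

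**What the plan says.** Section 5.4.13.1 handles proteinuria of 2 to 3 g/24 h by holding ramucirumab until protein falls below 2 g/24 h, "then resume at the -1 dose level". If protein above 2 g/24 h recurs, the next step is a stated dose and not a level: "A second dose reduction (to 5 mg/kg every other week) is permitted". No arm is named. The permanent stops follow: "Ramucirumab will be discontinued permanently if the protein level is" above 3 g/24 h, and likewise on a third occurrence above 2 g/24 h or if protein has not returned below 2 g/24 h within 2 weeks. Section 5.4.13.2 adds a stop for nephrotic syndrome.

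The dose levels are in 5.4.1f, introduced with "Dose reductions for all agents are as follows". For ramucirumab the table gives Arm B 8, 6 and 5 mg/kg, and Arm C 6, 5 and 4 mg/kg. The note below it closes the ladder: if "an agent is given at dose level (-2) and dose modification rules call for further reduction, the agent should be discontinued".

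Arm B no longer accrues. The Schema says "New patients are randomized to Arm A or Arm C", and section 8.3.5.2 sets the Arm C starting dose: "Patients will receive 6 mg/kg of IMC-1121B every 2 weeks".

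**The concern.** One sentence defines the first step relative to the arm's own ladder, and the next fixes the second step at a number that fits only one ladder. That number belongs to the arm that closed. On Arm C it coincides with the first step, so a patient who has already been cut to 5 mg/kg and relapses is told to take a second reduction to 5 mg/kg.

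What is at stake is the dose of the investigational drug in a patient with recurrent renal toxicity. Followed literally, 5.4.13.1 never uses Arm C's 4 mg/kg step for proteinuria: the first episode leads to 5 mg/kg, the second to 5 mg/kg, and the third ends ramucirumab. This also runs against the purpose of the redesign. Section 1.6 says that the modified regimen was to come with stricter handling of toxicity by dose modification.

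**Working it through.** The check is a lookup, followed by the percentage change at each step.

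**Inputs**

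- Rule for proteinuria (5.4.13.1): first reduction to level -1, second reduction to 5 mg/kg every other week, no arm specified.
- Ramucirumab ladder, Arm B (5.4.1f): 8 / 6 / 5 mg/kg.
- Ramucirumab ladder, Arm C (5.4.1f): 6 / 5 / 4 mg/kg. In the extracted text the arm label sits one line below this row. The row can only be Arm C's, because Arm B already has its own ramucirumab row and the starting dose of 6 mg/kg agrees with 5.1.3.1 and 8.3.5.2.

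**Formula.** Change at a step = (dose before − dose after) / dose before.

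| | Start | First reduction | Second reduction, 5.4.13.1 as written | Second reduction, level -2 in 5.4.1f |
|---|---|---|---|---|
| Arm B (closed) | 8 | 6 | 5 | 5 |
| Arm C (open) | 6 | 5 | 5 | 4 |

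**Arm B, where the stated figure reproduces.** Level -2 is 5 mg/kg, and the second step is (6 − 5)/6 = 16.7%. The rule and the table agree.

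**Arm C, where it does not.**

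- First step: (6 − 5)/6 = 16.7%. This is correct, because the rule uses the level.
- Second step as written: (5 − 5)/5 = 0%.
- Second step by the table: (5 − 4)/5 = 20%.
- Ratio of the written dose to the table dose: 5/4 = 1.25. The patient gets 25% more than level -2.

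**Could 5 mg/kg be a deliberate floor on Arm C?** Nothing in the documents says so. The sentence calls the step a reduction. The stop at a third occurrence fits a ladder with two real steps before it. The table gives Arm C a 4 mg/kg level, and other rules can reach it: the Grade 4 mucositis row in 5.4.5 lowers all agents by one level. Other text from the 8 mg/kg regimen also survives: 8.3.5.2 (Arm C) still mentions a dose of 8 mg/kg, and the reorder instructions in 8.3.9 are based on it. A sentence left unchanged when Arm C was added is the most likely explanation, but that is an inference.

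**The case against.** The strongest reply is that the slip exposes itself and does little harm. A step from 5 to 5 mg/kg is plainly not a reduction, so a pharmacist would turn to the table, which covers all agents and shows 4 mg/kg for Arm C. The wording is permissive. Even on a literal reading, ramucirumab is held until protein is below 2 g/24 h, the re-treatment dose is below Arm C's starting dose, and four separate conditions end ramucirumab for good.

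Most of this stands, and it is why the reach is limited. It does not make the sentence right. A rule specific to one toxicity that names an exact dose will normally be read as governing over a general table. A site that gives 4 mg/kg departs from 5.4.13.1, and a site that gives 5 mg/kg follows it without reducing anything. The protocol does not say which of the two prevails.

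A reader might also want to size the problem from section 1.4.1, where for the phase 1 study of dosing every 2 or 3 weeks "The most common (> 10%) treatment-related events were proteinuria (16.7"% of 24 patients. Multiplying that rate by the planned size of Arm C would count the wrong event. The rate covers any related proteinuria at 6 to 20 mg/kg. The slip needs two separate episodes above 2 g/24 h, neither above 3 g/24 h, and each recovering within 2 weeks. The list of related events of Grade 3 or higher for that study does not include proteinuria, although the list for the weekly study does. No headcount for the affected group can be supported.

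**Conclusion.** The rule is wrong as written, with limited reach. For Arm C the second reduction for proteinuria is 0% where the dose-level table gives 20%, and the dose is 25% above level -2. This follows directly from the two sections and rests only on reading the 6 / 5 / 4 row as Arm C's. It concerns Arm C patients with a second qualifying episode who meet none of the permanent stops. How many there would be is unknown.

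Two stronger readings should be resisted. First, a reader might infer that patients are left on ramucirumab without protection. They are not: the stops above 3 g/24 h, at a third occurrence, for no recovery within 2 weeks and for nephrotic syndrome are unaffected. Second, a reader might infer harm to the trial's inference. The sentence enters no sample-size, power or error-rate calculation, and nothing in the documents links it to an effect on PFS.

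**What to change.** In 5.4.13.1, replace the fixed dose for the second reduction with *the -2 dose level*. That gives 4 mg/kg on Arm C and leaves 5 mg/kg for any Arm B patient still on treatment, and it matches the way the first reduction is already expressed. Tell sites by memo.

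The cost is one phrase in an addendum and the memo. No patients, visits or procedures are added, and section 9 does not change.

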5.4.14 Cutaneous toxicity (Dose modifications for cetuximab only)

5.4.15	Infusion Reactions
--------	--------------------

Grade 1	Slow the infusion rate by 50%. Monitor the patient for worsening of the condition. For subsequent infusions, premedicate with diphenhydramine 50mg IV (or equivalent); additional premedication may be administered at the investigator's discretion.
Grade 2	Stop the infusion. Administer diphenhydramine 50mg IV (or equivalent), acetaminophen 650 mg orally for fever, and oxygen. Resume the infusion at 50% of the prior rate once the infusion reaction has resolved or decreased to grade 1; the infusion duration should not exceed 2 hours For subsequent infusions, premedicate with diphenhydramine 50mg IV (or equivalent); additional premedication may be administered at the investigator's discretion.
Grade 3 and Grade 4	Immediately and permanently discontinue the offending agent. Appropriate medical therapy including epinephrine, corticosteroids, intravenous antihistamines, bronchodilators, and oxygen should be available for use in the treatment of such reactions. Patients should be carefully observed until the complete resolution of all signs and symptoms.

For grade 1 or 2 reactions manifesting only as delayed drug fever, see Section 5.4.16.

For grade 4 or allergy related edema and angioedema and hypotension, permanently discontinue all medications.

For a second Grade 1 or 2 infusion reaction, administer dexamethasone 10mg IV (or equivalent); then, for subsequent infusions, premedicate with diphenhydramine 50mg IV (or equivalent), acetaminophen 650 mg orally, and dexamethasone 10mg IV (or equivalent).

# 5.4.16 Drug Fever

In the event of isolated drug fever, the investigator must use clinical judgment to determine if the fever is related to the study drug or to an infectious etiology. If a patient experiences isolated drug fever, for the next dose, pre-treat with acetaminophen or non-steroidal anti-inflammatory agent (investigator discretion); repeat antipyretic dose 6 and 12 hours after cetuximab infusion. The infusion rate will remain unchanged for future doses.

If a patient experiences recurrent isolated drug fever following premedication and post-dosing with an appropriate antipyretic, the infusion rate for subsequent dosing should be 50% of previous rate. If fever recurs following infusion rate change, the investigator should assess the patient's level of discomfort with the event and use clinical judgment to determine if the patient should receive further cetuximab. 5.4.17 Other Grade 3 and 4 Toxicities

For grade 3 events hold the offending agents until the toxicity resolves to grade  $\leq$  1. If grade 4, please discuss with the study chair.

- 5.5 Supportive Care
  - 5.5.1 All supportive measures consistent with optimal patient care will be given throughout the study.
  - 5.5.2 Diarrhea Management

For symptoms of diarrhea and/or abdominal cramping that occur at any time during a treatment cycle with irinotecan, patients will be instructed to begin taking loperamide. Loperamide should be started at the earliest sign of (1) a poorly formed or loose stool or (2) the occurrence of 1 to 2 more bowel movements than usual in 1 day or (3)an increase in stool volume or liquidity. Loperamide should be taken in the following manner: 4 mg at the first onset of diarrhea, then 2 mg every 2 hours around the clock until diarrhea-free for at least 12 hours. Patients may take loperamide 4 mg every 4 hours during the night. Loperamide should not be used for more than 48 hours. Patients should be provided with loperamide at the initial treatment visit so that they have sufficient supply on hand in case antidiarrheal support is required. Additional antidiarrheal measures may be used at the discretion of the treating physician. Patients should be instructed to increase fluid intake to help maintain fluid and electrolyte balance during episodes of diarrhea.

# 5.5.3 Antibiotics

Oral fluoroquinolone treatment should be initiated for any of the following:

- Diarrhea persisting for more than 24 hours despite loperamide
- ANC < 500/mcl (even in the absence of diarrhea or fever)
- Fever with diarrhea (even in the absence of neutropenia)
- Antibiotic therapy should also be initiated in patients who are hospitalized with prolonged diarrhea (even in the absence of neutropenia).
- 5.5.4 Lacrimation, rhinorrhea, miosis, diaphoresis, hot flashes, flushing, abdominal cramping, diarrhea, or other symptoms of early cholinergic syndrome may occur during or shortly after receiving irinotecan. Atropine, 0.25-1.0 mg IV or SC may be used to treat these symptoms. In patients with troublesome or recurrent symptoms, prophylactic administration of atropine shortly before irinotecan therapy may be considered. Additional antidiarrheal measures may be used at the discretion of the treating physician. Combination anticholinergic medications containing barbiturates or other agents (e.g., Donnatal®) should not be used because these may affect irinotecan metabolism. Anticholinergics should be used with caution in patients with potential contraindications (e.g., obstructive uropathy, glaucoma, tachycardia, etc.).

Rev. 6/14

[figure not shown]
Late diarrhea (e.g., developing more than 24 hours after irinotecan) should be managed with loperamide as described above.

- 5.5.5 Pegfilgrastim, epoetin and darbepoetin alfa may be administered at the treating investigator's discretion.
- 5.5.6 Dermatology Management

Suggested algorithm for management of cutaneous toxicity and paronychia:

In this protocol, acneiform rash and paronychia will be graded according to version 4.0 of the NCI-CTCAE definitions of rash/desquamation and nail changes. The patient should be followed until resolution of these toxicities.

Acneiform rash and paronychia should be managed according to the algorithms in Table 1-1 and Table 1-2. Cetuximab therapy treatment adjustments should be made according to Tables 1-3. Cetuximab dose reductions will be permanent (i.e., no dose re-escalations).

[figure not shown]

 STCN:
 Semisynthetic tetracyclines (doxycycline or minocycline)

 Topicals:
 Hydrocortisone 2.5% cream or alclomethasone 0.05% cream

 Oral Steroids:
 Methylprednisolone dose pack

Isotretinoin: Low doses (10-20 mg a day) or isotretinoin as a single agent

STCN:Semisynthetic tetracyclines (doxycycline or minocycline)Topicals:Hydrocortisone 2.5% cream or alclomethasone 0.05% creamOral Steroids:Methylprednisolone dose packIsotretinoin:Low doses (10-20 mg a day) or isotretinoin as a single agent

